8.3.7 ECG

Three consecutive (also called triplicate) 12-lead ECGs will be performed at defined timepoints throughout the study as per SoE ([Table 1](#)). Refer to [Table 4](#) for the detailed schedule of ECGs.

ECGs will be performed after the patient is resting for at least 5 minutes.

At timepoints coinciding with blood sample collection including PK, ECGs should be taken prior to blood collection.

If a patient experiences Torsade de Pointes, additional concomitant PK samples (i.e., unscheduled) should be collected.

Table 4. Schedule for Triplicate ECG Collection

Cycle	Day	ECG timepoint (window)
Screening	-	Any time within 28 days prior to C1D1
C1	D1	Pre-dose (preferably within 2 h prior to start of infusion) EOI (within 10 min prior to EOI) Post-dose* 4 h (\pm 15 min)
	D8	Post-dose* 168 h (\pm 48 h; but within 30 min prior to PK sample)
	D15	Post-dose* 336 h (\pm 48 h; but within 30 min prior to PK sample)
C2	D1	Pre-dose (within 30 min prior to PK sample) EOI (within 10 min prior to EOI) Post-dose* 4 h (\pm 15 min)
	D8	Post-dose* 168 h (\pm 48 h; but within 30 min prior to PK sample)
	D15	Post-dose* 336 h (\pm 48 h; but within 30 min prior to PK sample)
C3	D1	Pre-dose (within 30 min prior to PK sample) EOI (within 10 min prior to EOI)
C5, C7 ... every other cycle	D1	Pre-dose (within 30 min prior to PK sample)
EOT		Any time (but within 30 min prior to PK sample)
Unscheduled		Any time

Abbreviations: ECG, electrocardiogram; EOI, end of infusion; EOT, end of treatment; PK, pharmacokinetics.

*Post-dose timepoint is counted from start of infusion.

ECGs will be submitted for a central review. Submission instructions for the central review will be provided in a separate manual. Assessments will include determination of heart rate and rhythm and the PR, QRS, QT, QTcF, and QTcB intervals.

8.4 Pharmacokinetics, Pharmacodynamics, and Immunogenicity

PK, ADA, [REDACTED] will be collected as per SoE (Table 1). Additional biological samples may be collected by the Investigator when clinically indicated (e.g., at the time of significant AEs that are at least possibly related to the study drug) and may be used for PK, pharmacodynamics, [REDACTED]

When multiple samples are required at the same timepoint, collection of safety samples should be first followed by PK, then ADA, [REDACTED]

In order to better understand the disease, metabolic disposition, and pharmacologic behavior of loncastuximab tesirine in humans, samples remaining after primary analyses may be utilized for further analysis.

Biological samples may be retained for up to 10 years to further address scientific questions as new information in regards to the disease or the study drug becomes available.

For detailed instructions related to central laboratory sample collection, labeling, processing, storage, or shipment refer to the appropriate laboratory manual(s).

8.4.1 Pharmacokinetics

The concentration in serum of loncastuximab tesirine (total antibody), PBD-conjugated antibody, and unconjugated warhead SG3199 will be assessed by a central laboratory designated by the Sponsor using validated bioanalytical methods.

Approximately 6 mL of whole blood will be collected as per Table 1 and Table 5. Blood should be drawn from a vein away from the one used for study drug infusion.

PK samples must be stored at -70°C. Please refer to the laboratory manual for detailed instructions regarding specimen handling and shipment.

At timepoints coinciding with ECG collection, PK blood collection should occur immediately after the end of the ECG recording and, when applicable, after vital signs. If a patient experiences Torsade de Pointes, additional PK samples (e.g., unscheduled) should be collected.

Table 5. Sampling Schedule for PK and ADA

Cycle	Day	PK timepoint (window)	ADA timepoint (window)
C1	D1	Pre-dose (preferably within 2 h prior to start of infusion) EOI (-5 to +10 min) Post-dose* 4 h (± 10 min)	Pre-dose (preferably within 2 h prior to start of infusion)
	D8	Post-dose* 168 h (± 48 h)	-
	D15	Post-dose* 336 h (± 48 h)	Post-dose* 336 h (± 48 h)
C2	D1	Pre-dose (within 2h prior to start of infusion) EOI (-5 to +10 min) Post-dose* 4 h (± 10 min)	Pre-dose (within 2 h prior to start of infusion)
	D8	Post-dose* 168 h (± 48 h)	-
	D15	Post-dose* 336 h (± 48 h)	-
C3	D1	Pre-dose (within 2 h prior to start of infusion) EOI (-5 to +10 min)	Pre-dose (within 2 h prior to start of infusion)
C5, C7, ... every other cycle	D1	Pre-dose (within 2 h prior to start of infusion)	Pre-dose (within 2 h prior to start of infusion)
EOT		At any time during visit day	At any time during visit day
Unscheduled		Any time	Any time (if applicable, close to PK sample)

Abbreviations: ADA, anti-drug antibody; EOI, end of infusion; EOT, end of treatment; PK, pharmacokinetics.

*Post-dose timepoint is counted from start of infusion.

To understand the metabolic disposition of loncastuximab tesirine in humans, samples remaining after PK analysis is complete may be pooled among patients for potential metabolite identification.

8.4.2 Immunogenicity

Detection of ADAs will be performed by using a screening assay for identification of antibody positive samples/patients, a confirmation assay, and titer assessment, and will be performed using the Meso-Scale Discovery Electrochemiluminescence platform (MSD-ECL). If an ADA is confirmed, a functional assay for the assessment of the neutralizing capacity of the ADA will be performed.

Approximately 6 mL of whole blood will be collected as per [Table 1](#) and [Table 5](#). Blood should be drawn from a vein away from the one used for study drug infusion.

For patients who test positive for ADAs, an additional ADA sample will be requested for testing every 12 weeks following the EOT visit until the ADA titer falls to a background level.

ADA samples must be stored at -70°C. Please refer to the laboratory manual for detailed instructions regarding specimen handling and shipment.

8.5 Health-Related Quality of Life (HRQoL) Questionnaires

8.5.1 EuroQol-5 Dimensions-5 Levels (EQ-5D-5L)

EQ-5D-5L is designed as an international, standardized, generic instrument for describing and evaluating QoL (EuroQol Group, 1990). The EQ-5D-5L consists of two parts:

- The descriptive system: QoL is classified according to five dimensions: mobility, self-care, usual activities, pain/discomfort, and anxiety/depression. Each dimension comprises five levels of perceived problems (e.g., none, slight, moderate, severe, extreme).
- The visual analog scale (VAS): patients are asked to indicate their health state today on a VAS with the endpoints labeled ‘the best health you can imagine’ (score 100) and ‘the worst health you can imagine’ (score 0). Patients are asked to mark an “X” on the VAS to indicate their own health and then to report the score in a text box. If there is a discrepancy between where the patient has placed the X and the number he/she has written in the box, the number in the box is to be entered in the CRF together with a comment indicating the discrepancy.

8.5.2 Functional Assessment of Cancer Therapy - Lymphoma (FACT-Lym)

FACT-Lym is a lymphoma-specific subscale for the Functional Assessment of Cancer Therapy (FACT) questionnaire (Hlubocky FJ et al, 2013). It consists of 15 specific items that are used together with the core 27-item questionnaire FACT-G. The patient is asked to respond to each item with a score of 0–4, where 0 = not at all, 1 = a little bit, 2 = somewhat, 3 = quite a bit, and 4 = very much. A higher score indicates a worse level of QoL.

9 Statistical Considerations

Full details of the analysis plan, including a more technical and detailed elaboration of the statistical analyses, will be provided in the statistical analysis plan (SAP). [REDACTED]

9.1 Sample Size Calculation

Patients with DLBCL who have failed second line therapy have a very poor prognosis, with response to second-line salvage therapy ranging from 14-26%, with a median survival of 6.1 months (Seshadri et al., 2008; Crump et al., 2017). A treatment with a response rate of 20% would be a clinically meaningful option for this patient population.

The primary hypothesis is that the ORR based on central review for patients treated with loncastuximab tesirine is significantly greater than 20% (i.e., $H_0: p \leq 0.2$ vs. $H_a: p > 0.2$). This hypothesis will be tested at type I error of 0.05 (two sided).

Using nQuery exact test for single proportion, a sample size of 140 patients has >99% power to achieve a 1-sided significance level of 0.025 (2-sided significance level of 0.05). This sample size will provide adequate precision for observed ORR in the expected range. A 2-stage design will be used, with an interim analysis for futility on the first 52 patients. If ≥ 10 patients respond, the study will proceed to complete full enrollment. Enrollment will continue during the interim analysis; however, further enrollment will be halted if futility is confirmed to minimize exposure of patients in the study. With the null hypothesis that the true response rate is 0.2, and the alternative hypothesis that the true response rate is significantly greater than 20%, (40% is used for calculation), the design controls the type I error rate at 0.025 and yields a power of >99%.

9.2 Analysis Populations

- All Treated Population: All patients who receive at least 1 dose of loncastuximab tesirine. This population will be used in the primary analyses of efficacy and safety.
- Per-Protocol Population: All patients in the all-treated population without major protocol deviations, which will be further described in detail in the SAP.
- PK Population: All patients in the per-protocol population with at least 1 pre- (C1D1) and 1 post-dose valid assessment.
- Pharmacodynamics Population: All patients in the per-protocol population with at least 1 valid pharmacodynamics/ [REDACTED]

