9.8 Pharmacokinetic Analyses

The PK profile may include, but is not limited to, determination of: maximum concentration (C_{max}), area under the concentration-time curve from time zero to the end of the dosing interval ($AUC_{0-\tau}$), area under the concentration-time curve from time zero to infinity ($AUC_{0-\infty}$), clearance (CL), and accumulation index (AI).

[figure not shown]
PK parameters will be determined for all PK-evaluable patients using a non-compartmental method with Phoenix WinNonlin (Certara USA, Inc., Princeton, NJ, US) or other appropriate software. Supplemental population PK analyses will be undertaken and reported separately to characterize the PK parameters for the typical patient and to identify covariate factors which influence drug disposition.

Demographic data for the PK population will be summarized. Potential correlations of PK parameters to baseline characteristics and safety observations will be assessed but may be reported separately. In addition, the influence of loncastuximab tesirine PBD-conjugated antibody and unconjugated warhead SG3199 concentrations on the QTc interval will be assessed but reported separately.

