4.1.2 Per-Protocol Population

All patients in the all-treated population who met the inclusion/exclusion criteria, did not take a prohibited concomitant treatment, nor had other protocol deviation which have major impact on efficacy results.

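### The PK population is drawn from the per-protocol set, whose criteria do not test whether a concentration is valid

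*Protocol*

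**What the plan says.** Protocol 9.2 defines the PK population as "All patients in the per-protocol population with at least 1 pre- (C1D1) and 1 post-dose valid assessment". The parent set is, in the same section, "All patients in the all-treated population without major protocol deviations, which will be further described in detail in the SAP".

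SAP 4.1.2 supplies that detail in three conditions: the patient was eligible, took no prohibited treatment, and, in the SAP's words for the third, "nor had other protocol deviation which have major impact on efficacy results".

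The SAP has no PK population of its own. Sections 4.1.1 to 4.1.4 cover the all-treated, per-protocol, stem cell transplant and patient-reported outcome sets only. SAP 3.3 records no change to the protocol's statistical section, so the Protocol 9.2 definition stands. SAP section 6 still commits the PK endpoints to the study report.

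Protocol 9.8 then says "PK parameters will be determined for all PK-evaluable patients using a non-compartmental method", and separately "Demographic data for the PK population will be summarized". It does not define PK-evaluable or link it to the PK population. It also says "Supplemental population PK analyses will be undertaken and reported separately", and plans to look at PK parameters against baseline characteristics and safety observations. It names no analysis set for either.

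**The concern.** Describing the PK of three analytes is a secondary objective (Protocol section 3, Table 2). A PK set should be filtered on what makes a concentration usable: the dose given, the sample time, the assay result, and anything that distorts the measured level. Here the filter was written for a supportive efficacy analysis.

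Two things are at stake. The first is precision, since treated patients with usable concentrations can be set aside. The second is coverage. Patients who breached an organ-function or effusion criterion lie at the edge of the baseline range. If the correlations with baseline characteristics use the PK population, those patients would be missing from them, while safety itself is reported in all treated patients.

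**Working it through.** The documents give no figure on this point, so the check is mainly a comparison of definitions.

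**Step 1. Does each per-protocol condition test PK validity?**

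| Condition (SAP 4.1.2) | Breach unrelated to PK | Breach that can affect PK |
|---|---|---|
| Eligibility met | No tumor block or slides (Protocol 5.1, criterion 6) | Previous study drug, antibodies to a CD19 antibody, experimental drug within 14 days (Protocol 5.2, criteria 1, 2 and 18) |
| No prohibited treatment | Live vaccine in a late cycle (Protocol 6.7.2), for samples drawn before it | Possibly another anticancer or investigational agent (Protocol 6.7.2) |
| No other deviation materially affecting efficacy | Any such deviation that leaves dosing and sampling intact | Dose more than 15% off plan, or next cycle under 18 days after the last (SAP 4.3), but only if judged to affect efficacy |

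The eligibility condition has no materiality threshold, and the prohibited-treatment condition has no timing. By Protocol Table 5, a patient who reaches Cycle 3 has 5 scheduled PK samples in Cycle 1 and 5 in Cycle 2. One late prohibited treatment removes the patient and all 10. The filter can also err the other way: SAP 4.1.2 does not name a dosing error, so such a patient stays in unless the error is judged to matter for efficacy.

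**Step 2. How are comparable data handled?** ADA results use every patient tested (Protocol 9.9). The patient-reported outcome set starts from all treated patients (SAP 4.1.4). Neither passes through the per-protocol filter, and no reason is given for treating PK differently.

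**Step 3. Size, on an assumed rate.** Let d be the share of treated patients outside the per-protocol set who otherwise have valid samples. Patients lost = 140 × d. The ratio of standard errors of a mean = √(140 / remaining) = 1/√(1 − d).

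| Assumed d | Lost | Remaining | Ratio |
|---|---|---|---|
| 5% | 7 | 133 | 1/√0.95 = 1.026 |
| 10% | 14 | 126 | 1/√0.90 = 1.054 |
| 20% | 28 | 112 | 1/√0.80 = 1.118 |

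This assumes equal variability in those kept and lost. If some of those outside the set have PK-relevant breaches, the avoidable loss is smaller.

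**Step 4. Effect on the primary analysis.** None, because response rate uses the all-treated population. The stated power of over 99% reproduces: with 140 patients the exact test of 20% rejects at 39 or more responders (one-sided level 0.0158), with power 0.9990 at 40%. The PK definition does not enter that calculation.

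**The case against.** The strongest reply is that per-protocol exclusions are not all irrelevant to PK. Previous study drug could leave drug in the first pre-dose sample, and existing antibodies or a dosing error can change the measured levels. That stands. A reader might infer that no eligibility, treatment or efficacy deviation can affect a concentration, and the protocol's own exclusion criteria contradict that. The supportable statement is narrower: the conditions as written do not test for it.

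A reader might also infer that the PK-safety correlations will omit the excluded patients. Protocol 9.8 does not say so. It names no set for them, ties PK-evaluable to nothing, and leaves the population PK set unstated. The only analysis in 9.8 expressly tied to the PK population is a demographic summary. The loss from the non-compartmental analysis is therefore possible under the plan but not established.

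Nor is this a set chosen after seeing results. Two of the three conditions are prespecified categories. Only the third is open to judgement, in an open-label trial.

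Three further points stand. PK here is descriptive, with no test or precision target. The deviation rate is an assumption. A separate PK plan may exist: the SAP has no PK methods section and lists no PK tables, and part of the introduction to Protocol section 9 is redacted. None of this removes the explicit nesting in Protocol 9.2.

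**Conclusion.** The point holds as a definition that uses the wrong filter for a secondary objective. Followed as written, the plan can drop treated patients with valid concentrations from the PK population for reasons unrelated to PK.

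The size is unknown. It is 7 to 28 of 140 patients, with standard errors about 3% to 12% larger, if 5% to 20% fall outside the per-protocol set, all of them have otherwise valid samples, and the analysis uses the PK population as defined. The undefined term in Protocol 9.8 makes the last condition uncertain and is a gap in its own right. Primary response and safety conclusions do not change. This is a worthwhile improvement, not a threat to the trial.

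**What to change.** In SAP 4.1, add a PK population: all treated patients with valid PK assessments. Keep the present requirement for a Cycle 1 Day 1 pre-dose assessment and at least one post-dose assessment, unless a reason for dropping the pre-dose part is stated.

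Exclude individual samples, or a whole patient where every sample is affected, only for documented PK-relevant reasons. List those reasons before the PK results are reviewed. Candidates are dosing or sampling-time errors, previous study-drug exposure and pre-existing anti-CD19 antibodies.

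Tie PK-evaluable in Protocol 9.8 to this definition, and name the set for the PK-baseline and PK-safety correlations. Record the change in SAP 3.3 and align Protocol 9.2.

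The cost is wording. No patients, visits or samples are added, and the primary type I error and power are unchanged. Protocol 11.8 requires an amendment for any change in the study plan, so the protocol wording would need one.

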9.3 Interim Analysis for Futility

A single interim analysis is planned using Simon's 2-stage procedure. The purpose of this interim analysis is solely to determine if there is a sufficient ORR observed early in the study to warrant continuing study enrollment to completion. The interim analysis constitutes a futility analysis; it will not be used to stop the trial early for positive efficacy.

In the first stage of the study, an interim analysis will be performed at the time when the 52nd patient has two tumor assessments (approximately 12 weeks after start of study drug). Enrollment will continue during the interim analysis. If ≥ 10 patients respond, the study will proceed to the second stage. If < 10 patients respond, study enrollment will be halted.

Patients already enrolled may continue treatment for up to 1 year or until disease progression, unacceptable toxicity, or other discontinuation criteria (Section 7), whichever occurs first. Additionally, patients benefitting clinically at 1 year may continue treatment after a case by case review with the Sponsor.

9.4 Final Analysis

For primary and key secondary endpoints analyses, a database snapshot will be taken when all patients have a minimum of 6 months follow up after initial documented response. All efficacy, safety, and PK endpoints will be analyzed and reported in the clinical study report (CSR). Results of the population PK analysis will be reported separately.

The exact binomial test will be used in the final analyses for the primary endpoint because of the practical consideration that accrual cannot be limited to exactly 140 patients and because patients included in the interim analysis as non-responding may be included in the final analysis as responding if they experience a late response.

Follow-up analyses will be performed when all the patients complete the study per protocol. The results will be reported in a CSR addendum.

9.5 Demographics and Baseline Characteristics

The analyses include:

- Demographic information such as age, gender, ethnicity, and race (to the extent allowed by local regulations).
- Cancer medical history, which includes a complete history of all surgeries and significant diagnoses, and all cancer treatment, including surgery, radiation therapy, chemotherapy, etc.
- Any other relevant medical history.

9.6 Efficacy Analyses

Primary efficacy analyses will be based on response as determined by central review. Response reported by investigators will be used for sensitivity analyses.

9.6.1 Overall Response Rate

The ORR will be defined as the proportion of patients with a BOR of CR or PR. The overall response category will be derived based on response assessment performed on or before the start of subsequent anti-cancer therapy. For the primary ORR analysis in the all treated population, patients with a CR or PR will be counted as successes and all other patients (including those with missing response information) will be counted as failures.

The percentage of ORR with its 95% confidence interval (CI) will be presented. In contrast to CR, PR, or PD, a BOR of SD can only be made after the patient is on-study for a minimum of 35 days after the first dose of study drug. Any tumor assessment indicating SD before this time period will be considered as a non-evaluable for BOR if no assessment after this time period is available.

9.6.2 Duration of Response

DOR will be defined among responders (CR or PR) as the time from the earliest date of first response until the first date of either disease progression or death due to any cause. The date of disease progression will be defined as the earliest date of disease progression based on central review. For patients who have not progressed or died at the time of the analysis, censoring will be performed using the date of the last valid disease assessment. The data will be analyzed by the Kaplan-Meier method. The median duration of response and 95% CI will be presented. DOR will be analyzed by response subgroup (CR, PR). Further details will be outlined in the SAP.

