4.1 Overview

This is a Phase 2, multi-center, open-label, single-arm study of the efficacy and safety of loncastuximab tesirine used as monotherapy in patients with relapsed or refractory DLBCL. The study will enroll approximately 140 patients.

A 2-stage design will be used ([Simon, 1989](#)), with an interim analysis for futility using the data on the first 52 patients (see [Section 9.3](#)). If ≥ 10 patients respond (CR+PR), the study will proceed to complete full enrollment. Enrollment will continue during the interim analysis; however, further enrollment will be halted if futility is confirmed.

The duration of the study participation for each patient is defined as the time from the date of signed written informed consent to the completion of the follow-up period, withdrawal of consent, loss to follow-up, or death, whichever occurs first.

The study will include a Screening Period (of up to 28 days), a Treatment Period (cycles of 3 weeks), and a Follow-up Period (approximately every 12 week visits for up to 3 years after treatment discontinuation).

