4.9.2 Duration of Response

Duration of response will be defined for patients with CR or PR only as the interval between the date of initial documentation of a response and the date of the first documented evidence of progressive disease based on independent radiographic assessment or death, whichever occurs first. Clinical progression at EOT/EOS without radiographic assessment could be considered as an event in a sensitivity analysis. Patients who have the event after the start of subsequent anticancer therapy/procedure, or are progression-free and alive at the time of clinical cut-off, or have unknown status, will be censored at the last valid tumor assessment on or before the start of subsequent anticancer therapy/procedure or clinical cut-off time. When a subsequent anticancer therapy is used and progressive disease (based on radiographic or clinical progression at EOT/EOS) is observed within 6 days, they will be considered as the same visit (within the protocol specified +/-6 days visit window) and the patient will be counted as having an event (losing the response).

Patients with no post-baseline disease assessment will be censored on Day 1.

Duration of response will be estimated and displayed for the all-treated population using Kaplan-Meier methods (SAS[®] PROC LIFETEST). A Kaplan-Meier plot will be presented.

A sensitivity analysis of DOR will be conducted in which the DOR for patients undergo SCT will not be censored at SCT.

A sensitivity analysis of DOR per investigator assessments will also be conducted.

Subgroup analysis may be provided for disease subtype, disease stage, double/triple hit (yes/no), bulky disease (yes/no), GCB/ABC, transformed (yes/no), age group, response to the first line and/or most recent line of prior systematic therapy (relapse: CR+PR vs. refractory: SD+PD vs. other: NE + missing), best response to loncastuximab tesirine (CR/PR), and other relevant variables.

4.9.3 Time to Response:

Time to response (TTR) is defined among patients who achieve either CR or PR as BOR before the start of subsequent anticancer therapy or procedure as the time from the first dose to the initial documented response. For this subset of patients, TTR will be summarized using descriptive statistics.

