- 14. 2.1.9.2 Kaplan-Meier Plot of Duration of Response (Per-Protocol Population)
- 14. 2.1.9.3 Kaplan-Meier Plot of Duration of Response with Clinical Progression as an Event (All-Treated Population)
- 14. 2.1.9.4 Kaplan-Meier Plot of Duration of Response with Stem Cell Transplant not Censored (All-Treated Population)
- 14. 2.1.9.5 Kaplan-Meier Plot of Duration of Response by Primary Category of Disease Diagnosis (All-Treated Population)
- 14. 2.1.9.6 Kaplan-Meier Plot of Duration of Response by Double/Triple Hit (Yes/No) (All-Treated Population)
- 14. 2.1.9.7 Kaplan-Meier Plot of Duration of Response by First Line Prior Systemic Therapy Response Group (All-Treated Population)
- 14. 2.1.9.8 Kaplan-Meier Plot of Duration of Response by Number of Prior Systemic Therapy Line Group (All-Treated Population)
- 14. 2.1.9.9 Kaplan-Meier Plot of Duration of Response by Last Line Prior Systemic Therapy Response Group (All-Treated Population)
- 14. 2.1.9.10 Kaplan-Meier Plot of Duration of Response by CR and PR (All-Treated Population)
- 14. 2.1.9.11 Kaplan-Meier Plot of Duration of Response by Age Group (All-Treated Population)
- 14. 2.1.9.12 Kaplan-Meier Plot of Duration of Response by Transformed and De novo (All-Treated Population)
- 14. 2.1.9.13 Kaplan-Meier Plot of Duration of Response by Disease Stage (All-Treated Population)

14. 2.1.9.14 Kaplan-Meier Plot of Duration of Response by Bulky Disease (Yes/No) (All-Treated Population)

14. 2.1.9.15 Kaplan-Meier Plot of Duration of Response by Subtype of Germinal center B-cell/Activated B-cell (All-Treated Population)

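### Splitting DOR by best response (CR vs PR) favours CR to the extent that CRs follow a first PR; the plan should add a split by status at first response or a landmark

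*Protocol*

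**What the plan says.** - **Clock.** Protocol 9.6.2 measures DOR among responders as "the time from the earliest date of first response until the first date of either disease progression or death due to any cause". SAP 4.9.2 likewise starts at the initial documented response. The start is the first CR or PR, whichever is seen first.
- **Grouping.** The same protocol section says "DOR will be analyzed by response subgroup (CR, PR") without saying when the category is fixed. SAP 4.9.2 settles this by listing "best response to loncastuximab tesirine (CR/PR") among the DOR subgroups.
- **Output.** SAP Appendix 2 lists figure 14.2.1.9.10, "Kaplan-Meier Plot of Duration of Response by CR and PR (All-Treated Population").
- **Window for best response.** Protocol 9.6.1 and SAP 4.9.1 use every assessment up to the start of subsequent anticancer therapy.
- **Scans.** Protocol 8.1 schedules imaging at Weeks 6 and 12, then every 9 weeks on treatment.

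Neither document has a landmark, a time-dependent analysis, a split by status at first response, or a caution on reading the figure. RFS (Protocol 9.6.4, SAP 4.9.5) runs from first CR, but only for patients who reach CR.

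**The concern.** The group label can be set after the clock has started. For a patient whose first response is PR, entry to the CR group requires being progression-free at a later scan. The time from first PR to CR is therefore guaranteed event-free, and it is credited to CR. Patients who progress before they could convert remain in PR. This is immortal-time bias, and it pushes the two curves apart in a known direction.

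What is at stake is the reading of one secondary figure. The comparison invites a statement about durability by depth of response. Protocol 1.1 itself contrasts durable CRs with short PRs (2.1 months) for an approved CAR-T therapy. Medians from figure 14.2.1.9.10 could be read in the same way, although part of any gap may come from the grouping.

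**Working it through.** **The plan's own figure.** The documents give no number for DOR by CR and PR. The nearest stated figure is the power, and it sets the expected number of responders. For n = 140 and a 20% null, the smallest r with P(X ≥ r | 0.20) ≤ 0.025 is 39 (exact level 0.0158). The power is P(X ≥ 39 | 0.40) = 0.9990, so the stated >99% reproduces. At 40% ORR there would be 140 × 0.40 = 56 responders.

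**Inputs from the documents**
- On-treatment scans after a first response at Week 6 fall at Weeks 12, 21, 30, 39, 48 and 57, i.e. 6, 15, 24, 33, 42 and 51 weeks after response (Protocol 8.1).
- The snapshot requires at least 6 months of follow-up after response (SAP 6).
- The Phase 1 DLBCL CR share among responders was 22/38 = 58% (Protocol 1.3).

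**Assumptions (not in the documents)**
- Time from first response to progression or death is exponential with a median of 6 months (26.1 weeks), the same for every responder, so depth has no effect.
- 35% of responders are in CR at first response.
- A PR patient still event-free at a scan converts with probability p, from 0% to 25%.
- Follow-up is uniform over 6 to 12 months, and the on-treatment scan schedule continues.

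**Result.** Responders were simulated and split by best response seen before censoring. Kaplan-Meier medians in months (a rerun agreed to within 0.1):

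| Conversion per scan | CR | PR | Gap |
|---|---|---|---|
| 0% | 6.0 | 6.0 | 0 |
| 2% | 6.4 | 5.8 | 0.6 |
| 5% | 6.8 | 5.4 | 1.4 |
| 15% | 7.6 | 4.3 | 3.3 |
| 25% | 7.8 | 3.2 | 4.6 |

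**Which rows are plausible?** The final CR share can be checked by hand. With S(t) = 2^(−t/26.1), the chance of being event-free at the six scans is 0.853, 0.671, 0.529, 0.416, 0.328 and 0.258. The chance that a first PR becomes a CR is Σ p(1−p)^(k−1) S(t_k). At p = 15% this is 0.15 × (0.853 + 0.570 + 0.382 + 0.256 + 0.171 + 0.114) = 0.352. The CR share is then 0.35 + 0.65 × 0.352 = 58% with complete follow-up.

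Under 6 to 12 months of follow-up, the last three terms are multiplied by the chance of still being under observation: (52.2 − 33)/26.1 = 0.736, then 0.391 and 0.046. The conversion chance falls to 0.310 and the share to 55%. The 15% row is therefore close to Phase 1. The 25% row gives 67% with complete follow-up, above Phase 1. Phase 1 does not identify p, because a higher CR share at first response with little conversion fits 58% equally well.

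**Second model.** Here progression is seen only at scans, 80% of first responses are at Week 6, and the true median is 5 months:
- 39% of CRs late: 7.6 (CR) vs 4.1 (PR) months, PR/CR progression-rate ratio 1.81.
- 16% late: ratio 1.32.
- 8% late: ratio 1.17.
- None late: ratio 0.99.

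**Do the remedies work?**
- Split by status at first response: rate ratios 0.98 to 1.02 in every scenario of the second model. A nominal 5% log-rank test with 56 responders rejected 4.5% to 5.7% of the time.
- Week 12 landmark in the first model, with complete follow-up: equal medians (5.97 to 6.01 vs 6.00 months).
- Landmark at 15 weeks after first response in the second model: ratios 0.98 to 1.11, so a small residue can remain.

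**Cost of the Week 12 landmark.** Week 6 responders lost before Week 12 are 1 − 2^(−6/26.1) = 15% at a median of 6 months. At 10 months (43.5 weeks) they are 1 − 2^(−6/43.5) = 9%.

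**The case against.** - **Conversion may be rare.** The documents do not say how often a CR follows a first PR. Protocol 2.2 reports rapid onset of response (median 2 cycles). If nearly every CR is present at the first responding scan, the gap is small or nil. This stands, and it is why the point is conditional. The median of 2 cycles describes onset of response, not time to CR, so it does not show that conversion is absent.
- **Nothing is tested.** SAP 4.9.2 says DOR subgroups may be provided, and neither document plans a CR-vs-PR test or claim. This stands and limits the weight. A descriptive label does not, however, remove the bias from the medians shown.
- **RFS already covers CR durability.** It does, without the credited PR time. It offers no PR comparison and so cannot correct the figure.

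A reader might infer more than the documents support:
- *That any CR-PR gap in this trial would be an artefact.* A true effect of depth may also exist; the grouping only makes the two inseparable in this figure.
- *That the bias is certain and large, for instance about 8 vs 3 months.* Such figures need 25% conversion per scan and no censoring. The snapshot rule allows follow-up as short as 6 months after response, and that conversion rate overshoots the Phase 1 CR share.
- *That the main efficacy results are affected.* ORR does not use this split, and overall DOR pools all responders from first response.

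**Conclusion.** The point holds conditionally. Under SAP 4.9.2 the CR/PR label can be fixed after the DOR clock starts, and no planned analysis corrects for it. If some CRs follow a first PR, the figure overstates CR durability relative to PR.

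The size rests on an assumed conversion rate. Under the 6-month model the gap in medians runs from none at 0% per scan, through 1.4 months at 5%, to 3.3 months at 15%, the setting closest to the Phase 1 CR share when 35% of responders are in CR at first response. The direction is firm whenever conversion occurs; the amount is not known until conversions are counted. The consequence is confined to one secondary descriptive comparison, so this is an optional, cheap improvement.

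**What to change.** 1. In SAP 4.9.2, add a Kaplan-Meier analysis of DOR by response status at first response (CR or PR at the scan that starts the clock). It keeps every responder and removes the artefact. Its downside is that late converters count as PR, so it does not show what a later CR adds.
2. Instead or in addition, add a Week 12 landmark: among responders event-free and under follow-up at the Week 12 scan, Kaplan-Meier time from Week 12 by status at Week 12. It omits responders who fail before Week 12 (about 9% to 15% of Week 6 responders at true medians of 10 and 6 months) and those who first respond later.
3. Keep figure 14.2.1.9.10 and footnote it as descriptive, stating that the groups are set by best response and giving the number of CRs that followed a first PR.
4. Leave RFS as the measure of CR durability.

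The cost is one or two figures and a footnote. The response dates needed are already collected, no pre-specified analysis is removed, and no visit or procedure changes.
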